9.4 STATISTICAL ANALYSES

9.4.1 GENERAL APPROACH

An independent statistician using standard statistical techniques will determine statistically significant differences in the trial measurement data. Statistical significance will be set at the nominal level of $p<0.05$. Plasma concentrations (genistein aglycone; free genistein) will be measured (AUC, C_{max} , T_{max} , $T_{1/2}$) and plasma kinetic rate will be calculated using standard procedures and statistical analyses (e.g., AUC using the linear trapezoidal formula and $T_{1/2}$ using linear regression). Data will be summarized by descriptive statistics (mean/medians and standard errors/confidence intervals for continuous response variables and distribution tables or histograms for discrete response variables).

Baseline characteristics will be compared using matched-pair t-tests. The computed change from baseline will be calculated for all measured variables and expressed as the mean change from baseline

and accompanying standard deviation (SD) of the change from baseline. Repeated measures ANOVA tests will be used to compare changes in scores for each variable between each treatment group. Matched pair t-tests will be used to compare the change scores within each treatment group. All data analyses will be conducted on the subjects who completed the study treatment periods and statistical significance will be set at $p<0.05$.

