9.4.2 ANALYSIS OF THE PRIMARY EFFICACY ENDPOINT(S)

Blood counts, serum chemistry, urinalysis, ECGs, vital signs, and PTT/INR for the study cohorts will be reported as a mean \pm SD at each of the timepoints listed in the **SoA, Section 1.3**. An analysis of covariance (ANCOVA) to compare the cohorts after adjusting for "baseline" (the adjustment covariate) will be completed. Analysis will be performed in individual subjects to identify changes in safety measurements relative to baseline, and between cohorts at the timepoints listed in the **SoA, Section 1.3** to identify any potential dose-response relationships.

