9.4.5 BASELINE DESCRIPTIVE STATISTICS

Baseline characteristics, such as subject age, vital signs, laboratory results, and BMI will be compared between the dosing cohorts using descriptive statistics. ANOVA analysis will be used to compare each parameter between the study cohorts at baseline.

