5.4. Pharmacodynamics (PD) Population

The PD Population will include all subjects who receive at least 1 dose of BIO 300 Oral Powder and have sufficient, valid serum samples to estimate key parameters for at least 1 of the days of sampling. PD summaries will be based on the PD population.

6. Safety Monitoring Committee

A Safety Monitoring Committee (SMC) will review safety and PK data (when available) during the conduct of the study. After each cohort in the SAD study, the SMC will make decisions on proceeding with dose escalation, adding additional subjects to the current cohort, and possible dose adjustments. The SMC may also recommend stopping the study, suspending enrollment or significant changes to the dosing regimen and/or enrollment if warranted by safety data. The SMC will immediately communicate this recommendation to Humanetics for review and determination of a final decision. SMC data reviews are

not considered interim analyses and do not necessitate adjusting of the alpha level for multiple statistical hypothesis tests.

7. Statistical Methods

Unless stated otherwise, the term “descriptive statistics” refers to the number of subjects (n), mean, median, standard deviation (STD), minimum (min), and maximum (max) and standard errors/confidence intervals for continuous response variables and distribution tables or histograms for discrete response variables. Min and max values will be rounded to the precision of the original value, means and medians will be rounded to 1 decimal place greater than the precision of the original value, and STDs will be rounded to 2 decimal places greater than the precision of the original value. Percentages will be rounded to the nearest whole number (zeros are not displayed) with values of “< 1%” and “> 99%” shown as necessary for values falling near the boundaries.

The computed change from baseline will be calculated for all measured variables and expressed as the mean change from baseline + STD of the change from baseline. Analysis of covariance will be used to compare dosage groups on “change from baseline” measures (with baseline measurement considered as an adjustment covariate).

Unless otherwise note, all data collected during the study will be included in data listings and will be sorted by study cohort, subject number and then by visit for each subject number.

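### Protocol 9.4.1 contradicts the more specific text twice: change-score repeated-measures ANOVA against the ANCOVA of 9.4.2 and SAP 7, and matched-pair baseline tests where no pairs exist

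*Combined protocol and SAP*

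**What the plan says.** **Change between cohorts.** Protocol 9.4.1 (General Approach): "Repeated measures ANOVA tests will be used to compare changes in scores for each variable between each treatment group". No baseline covariate is named. Protocol 9.4.2, which deals with blood counts, chemistry, urinalysis, ECGs, vital signs and clotting, gives a different method: "An analysis of covariance (ANCOVA) to compare the cohorts after adjusting for" the baseline value. SAP Section 7 agrees with 9.4.2: "Analysis of covariance will be used to compare dosage groups on" change from baseline, with the baseline measurement as covariate. The SAP does not mention repeated-measures ANOVA.

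**Baseline.** Protocol 9.4.1: "Baseline characteristics will be compared using matched-pair t-tests". It states neither the groups compared nor how pairs are formed. Protocol 9.4.5, and SAP 8.3 in the same words: "ANOVA analysis will be used to compare each parameter between the study cohorts at baseline". The list in SAP 8.3 includes gender, race and ethnicity.

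**Within cohorts.** Protocol 9.4.1: "Matched pair t-tests will be used to compare the change scores within each treatment group".

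**Which text governs.** Neither document says. Protocol 4.4 has the sponsor analyse the data under protocol Section 9, and protocol 10.1.11 bases the first publication on analysis as the protocol lays down. The SAP introduction says that it details the planned methods, but it calls the protocol a companion document and cites version 1.0. The protocol's amendment history runs to version 2.0.

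**The concern.** Two methods stand in the plan for one comparison. They answer slightly different questions and give different p-values. An analysis of raw change leaves chance baseline differences between cohorts in the result, whereas ANCOVA adjusts for them. With 6 subjects per cohort those differences are not small. Protocol 9.4.2 uses the between-cohort comparison to look for dose-response in safety measurements, so the choice affects what the report says about dose and safety.

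The matched-pair baseline rule is a separate fault. A paired test needs two linked values. Baseline is one screening value per subject (protocol 9.1, SAP 7.1), so a subject has no second baseline value to pair with it. Across cohorts the subjects are different people: the trial is not randomised, prior use of the test article is an exclusion, and no matching is described. Any pairing would be arbitrary.

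**Working it through.** **Inputs from the documents.** Four single-dose cohorts with at least 6 completers each, and one multiple-dose cohort with at least 8 (protocol 9.2); nominal 0.05 level (protocol 9.4.1, SAP 7.5). The only figures to reproduce are the counts: 4 × 6 = 24, and 24 + 8 = 32. Both agree with the plan.

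**Assumptions.** The documents give no SD, effect size or baseline-to-follow-up correlation ρ. I take SD 1 at every visit, ρ from 0.3 to 0.9, two-sided testing, and cohorts that differ at baseline only by chance.

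**Step 1: why the tests differ (one follow-up visit).** Per-subject error variance is 2(1 − ρ) for raw change and 1 − ρ² for ANCOVA. The ratio of ANCOVA to change is (1 − ρ²) / [2(1 − ρ)] = (1 + ρ)/2, which is 0.65, 0.75, 0.85 and 0.95 at ρ = 0.3, 0.5, 0.7 and 0.9. ANCOVA uses one more degree of freedom (F on 3 and 19 instead of 3 and 20). Its advantage therefore shrinks as ρ rises.

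The SD of the chance baseline gap between two cohorts of 6 is √(2/6) = 0.58 SD. Raw change carries (1 − ρ) of that gap, so at ρ = 0.5 a gap of this size gives 0.58 × 0.5 = 0.29 SD of spurious difference.

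**Step 2: power, one follow-up visit, 1.2 SD shift in one of four cohorts of 6 (6,000 simulated trials per setting).**

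| ρ | Change-score ANOVA | ANCOVA | Gain |
|---|---|---|---|
| 0.3 | 34% | 48% | 14 points |
| 0.5 | 47% | 57% | 10 points |
| 0.7 | 71% | 76% | 5 points |

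**Step 3: the repeated-measures form.** Two follow-up visits, with the shift rising in equal steps across cohorts to 1 SD at the top dose (5,000 trials per setting). The repeated-measures group effect equals a one-way ANOVA on each subject's mean change; ANCOVA uses the same mean change with baseline as covariate.

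| ρ | RM ANOVA power | ANCOVA power | Verdicts differ, 1 SD shift | Verdicts differ, no effect | Either significant, no effect |
|---|---|---|---|---|---|
| 0.3 | 0.25 | 0.42 | 27% | 6.4% | 8.2% |
| 0.5 | 0.33 | 0.46 | 23% | 5.8% | 7.9% |
| 0.7 | 0.52 | 0.59 | 18% | 4.2% | 6.8% |
| 0.9 | 0.96 | 0.96 | 2% | 2.6% | 6.0% |

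With no effect, each test alone rejects in 4.3 to 5.2% of trials.

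**Step 4: the pairing.** For two independent cohorts of 6 there are 6! = 720 pairings. Over 2,000 data sets with no true difference, the median smallest paired p-value is 0.13 and the median largest is 0.63. In 36% of data sets some pairings give p < 0.05 and others do not. Cohorts of 6 and 8 cannot be fully paired.

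**The case against.** The strongest reply is that the choice has in substance been made. Section 9.4.1 is only the general approach. Section 9.4.2 is specific to the safety measurements and names ANCOVA, and so does the SAP. A reader might infer that the analysis is undefined; the documents do not support that. What stands is that 9.4.1 applies its method to every variable, nothing withdraws it, and protocol 4.4 and 10.1.11 send the analyst to a protocol section that contains both methods.

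A reader might also infer that the false-positive rate is inflated. Nothing in the plan permits reporting whichever test is significant. The 6 to 8% arises only if that were done, and with no effect the two verdicts disagree in only 3 to 6% of trials.

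On the pairing, 9.4.1 does not say that the baseline test runs between cohorts. That is an inference, though the screening-only definition of baseline leaves little else. The 36% is not a false-positive rate: a pairing fixed without sight of the data keeps the 5% level and mainly wastes degrees of freedom. Protocol 9.4.5 and SAP 8.3 already give a usable method for continuous baselines.

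Two further limits stand. ANCOVA is not automatically unbiased if these non-randomised cohorts truly differ at baseline; the simulations assume only chance differences. The literal reading that SAP 8.3 applies ANOVA to gender, race and ethnicity is softened by SAP Section 7, which assigns discrete variables to distribution tables or histograms.

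**Conclusion.** The concern holds as two contradictions inside the plan, both originating in protocol 9.4.1. The matched-pair baseline rule cannot be carried out meaningfully as written. The repeated-measures ANOVA competes with the ANCOVA named in two more specific places, without a stated order of precedence.

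The size is modest. ANCOVA gains about 5 to 14 points of power in the single-visit setting at correlations of 0.3 to 0.7, and nothing at 0.9. All of this rests on assumed correlations and effects. There is no loss of error control if one test is fixed in advance.

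A reader might go further and see a risk to dose decisions. The documents do not support that: protocol 7.5 escalates on DLT counts and committee review, and SAP 10.3 to 10.5 summarise laboratory, vital-sign and QTc data descriptively. The effect is confined to the reported between-cohort safety comparisons. The contradiction is nevertheless worth correcting, because the trial is open label and a choice left until analysis could be made with the results in view.

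**What to change.** In protocol 9.4.1:

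- Delete the repeated-measures ANOVA sentence and the matched-pair baseline sentence.
- State that change is compared between cohorts by the ANCOVA of 9.4.2 and SAP Section 7, and that the SAP governs where the two documents differ.
- Keep the within-cohort matched-pair tests, where each subject is compared with his or her own baseline.

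For baseline, follow protocol 9.4.5 and SAP 8.3. In SAP 8.3, limit the ANOVA to continuous parameters and summarise gender, race and ethnicity by counts.

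Dropping the baseline ANOVA altogether, or replacing the ANCOVA with a mixed model over all visits, would be a matter of preference; the contradiction does not require either.

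The cost is wording only. No data collection, sample size or schedule changes, and there is slightly less analysis to run.

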7 STUDY INTERVENTION DISCONTINUATION AND PARTICIPANT DISCONTINUATION/WITHDRAWAL

7.1 STOPPING CRITERIA FOR DISCONTINUATION OF THE STUDY INTERVENTION

Discontinuation of a subject and early stopping of the study intervention will be based on the following unacceptable adverse events (AEs) and must be attributable to the investigational drug BIO 300 Oral Powder (i.e., possibly, probably or definitely related to the study drug) to constitute a Dose-Limiting Toxicity (DLT).

- Non-hematologic toxicities of Grade 3 or higher, with the following exceptions:
 - anorexia
 - fatigue
 - infection without neutropenia

- Grade 3 AST/ALT elevations ≤ 7 days
- Grade 3 or 4 electrolyte abnormalities that are corrected to Grade 2 or less in less than 48 hours.
- Occurrence of a VTE (DVT or pulmonary embolism).

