7.2 DISCONTINUATION OF STUDY INTERVENTION

Discontinuation from BIO 300 Oral Powder does not mean discontinuation from the study, and the remaining study procedures should be completed as indicated by the study protocol. If a clinically significant finding is identified (including, but not limited to changes from baseline) after enrollment, the Principal Investigator or qualified designee will determine if any change in participant management is needed. Any new clinically relevant finding will be reported as an adverse event (AE).

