7.3 PARTICIPANT DISCONTINUATION/WITHDRAWAL FROM THE STUDY

Subjects are free to withdraw from participation in the study at any time upon request. The Principal Investigator may discontinue or withdraw a subject from the study for the following reasons:

- Pregnancy (see **Section 8.4.8**). Women of childbearing potential must perform a pregnancy test in case of delayed menstruation and stop treatment immediately in case of positive result.
- Significant study intervention non-compliance.
- Any clinical adverse event (AE), laboratory abnormality, or intercurrent illness that, in the opinion of the Principal Investigator, indicates that continued participation in the study is not in the best interest of the participant.
- If the participant meets an exclusion criterion (either newly developed or not previously recognized) that precludes further study participation.
- If the participant withdraws their informed consent.

The reason for participant discontinuation or withdrawal from the study will be recorded on the Case Report Form (CRF). Subjects who sign the informed consent form and are randomized but do not receive the study intervention may be replaced.

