9.3 POPULATIONS FOR ANALYSES

All participants will be analyzed. The ITT dataset is the primary dataset for analysis. As a guide, analyses may include, but are not limited to, any or all of the following:

- Intention-to-Treat (ITT) Analysis Dataset: all participants
- Safety Analysis Dataset: participants who took at least one dose of BIO 300 Oral Powder

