5.2. Safety Analysis Dataset

All study participants who receive at least one dose of BIO 300 Oral Powder. This analysis set will be used to summarize all safety endpoints.

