8.3. Baseline and Demographic Characteristics

Demographic and baseline characteristic data will be summarized with descriptive statistics for age, gender, race, ethnicity, height, weight, BMI, vital signs and laboratory results. ANOVA analysis will be used to compare each parameter between the study cohorts at baseline.

9. Endpoint Analyses

All observations available in the study database will be included in endpoint analysis regardless of subjects' aggregate exposure to BIO 300 Oral Powder, use of concomitant medications, or violations of the protocol. Relevant data supporting efficacy analyses will be listed by subject.

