9.3. Analysis for Blood-Based Biomarkers

Blood-based biomarkers will be identified by extracting RNA from whole blood samples and performing transcriptome analysis to determine differential gene expression. Transcriptome analysis will be conducted by paired-end RNA sequencing. After investigating the quality of the raw sequencing data, sequence reads will be trimmed to remove possible adapter sequences and nucleotides with poor quality using Trimmomatic v.0.36. The trimmed reads will be mapped to the Homo sapiens reference genome available on ENSEMBL using the STAR aligner v.2.5.2b. The STAR aligner is a splice aligner that detects splice junctions and incorporates them to help align the entire read sequences. Binary Alignment Map (BAM) files will be generated as a result of this step. Unique gene hit counts will be calculated by using feature counts from the Subread package v.1.5.2. Only unique reads that fell within exon regions will be counted.

After extraction of gene hit counts, the gene hit counts table will be used for downstream differential expression analysis. Using DESeq2, a comparison of gene expression between the groups of samples will be performed. The Wald test will be used to generate p-values and Log2 fold changes. Genes with adjusted p-values < 0.05 and absolute log2 fold changes > 1 will be called as differentially expressed genes for each comparison. A gene ontology analysis will be performed on the statistically significant set of genes by implementing the software GeneSCF. The goa_human GO list will be used to cluster the set of genes based on their biological process and determine their statistical significance. A principal component analysis (PCA) will be performed using the "plotPCA" function within the DESeq2 R package. This plot will show the samples in a 2D plane spanned by their first two principal components. The top 500 genes, selected by highest row variance, will be used to generate the plot.

10. Safety Analyses

Summaries of safety endpoints will include data collected from the safety analysis dataset. Relevant data supporting safety analyses will be listed by subject.

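### Protocol 9.4.1 limits all analyses to treatment completers, against protocol 9.3 and the SAP's dosed set; separately, SAP 10.3 plans no urinalysis analysis although urinalysis is scheduled after dosing (minor)

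*Combined protocol and SAP*

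**What the plan says.** **Analysis set.** Protocol 9.4.1 closes with the rule that "All data analyses will be conducted on the subjects who completed the study treatment periods", with no exception for safety. Protocol 9.3 says every participant is analysed and that "The ITT dataset is the primary dataset for analysis"; it also defines a safety set of those who took at least one dose. SAP 5.2 defines the same dosed set and adds "This analysis set will be used to summarize all safety endpoints". SAP section 9 begins "All observations available in the study database will be included in endpoint analysis regardless of" aggregate exposure, among other things. SAP section 10 repeats that "Summaries of safety endpoints will include data collected from the safety analysis dataset". Neither document has a precedence clause.

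**Who stops early.** Protocol 7.1: "Discontinuation of a subject and early stopping of the study intervention will be based on the following unacceptable adverse events", which must be attributable to the drug. Protocol 7.2: "Discontinuation from BIO 300 Oral Powder does not mean discontinuation from the study, and the remaining study procedures should be completed". Protocol 7.3 lets the investigator withdraw a subject for "Any clinical adverse event (AE), laboratory abnormality, or intercurrent illness that, in the opinion of the Principal Investigator", makes continued participation undesirable for that person.

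**Urinalysis.** SAP 10.3 gives eligibility as the sole purpose of urinalysis and rules out any analysis of it. Protocol 8.1 and 9.1 and SAP 9.1 count urinalysis as safety data. Protocol 9.4.2 has it reported as mean and SD at each scheduled timepoint. The Schedule of Activities (1.3) marks it in the last column, Day 13 of the six-day cohort.

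**The concern.** The two rules on the analysis set cannot both be followed. The completer rule matters because completing treatment is not independent of the outcome: 7.1 ties stopping to drug-attributable toxicity. Because 7.2 keeps a stopped subject on study while 7.3 permits withdrawal, later safety data may exist for some stopped subjects and not for others. Where they exist, a completer rule discards them from the change-from-baseline summaries of laboratory values, vital signs and ECGs. In the only repeated-dose cohort, those are the subjects whose values one would most want to see.

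The urinalysis issue is independent of this one. Here the SAP, carried out as written, omits a summary that the protocol specifies, for a reason that a post-dose test contradicts. A test on Day 13 cannot decide eligibility for dosing that ended on Day 6.

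**Working it through.** **Part (a): the completer restriction**

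Inputs from the documents:
- Planned completers: 4 cohorts × 6 = 24 single-dose, plus 8 six-day, gives 32. This reproduces the synopsis. The sample size is not power-based, and no dropout rate is given.
- Six-day cohort: 10 recruited, at least 8 completing (synopsis; SAP section 4), with six consecutive daily doses (6.1.2). A subject can therefore be dosed without completing treatment.
- Single-dose cohorts: one dose is the whole treatment, so dosed subjects and completers coincide and nothing shifts.
- Six-day safety bloods after first dosing: Days 3, 6 and 13 (8.3). A subject who stops drug on Day 3 and stays on study under 7.2 still contributes Days 6 and 13.

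Assumptions: n dosed, of whom n − 1 complete with mean change 0 and SD 1, and one stops early with post-dose data and a change of k SD. No document figure fixes n or k, so a range is shown.

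Formulas for the dosed set:
- mean = k/n
- SD = √{[(n − 2) + k²(n − 1)/n]/(n − 1)}
- paired t = mean/(SD/√n), on n − 1 degrees of freedom

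For n = 9 (8 completers plus 1) and k = 3: mean = 3/9 = 0.33; SD = √[(7 + 9 × 8/9)/8] = √(15/8) = 1.37.

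| k (n = 9) | Dosed-set mean | Dosed-set SD | Completers: mean, SD |
|---|---|---|---|
| 0 | 0 | 0.935 | 0, 1.00 |
| 1 | 0.11 | 0.993 | 0, 1.00 |
| 2 | 0.22 | 1.15 | 0, 1.00 |
| 3 | 0.33 | 1.37 | 0, 1.00 |
| 5 | 0.56 | 1.91 | 0, 1.00 |

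With 10 dosed, the means for k = 2, 3 and 5 are 0.20, 0.30 and 0.50.

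Direction:
- Excluding the stopped subject shrinks the SD only if k²(n − 1)/n > 1, that is k > √(n/(n − 1)) = √(9/8) = 1.06 at n = 9. For smaller k, exclusion raises it.
- For completers' mean m and stopped subject's change x, the dosed mean is m + (x − m)/n. With m = 0.5, x = 0 and n = 9 it is 0.5 − 0.5/9 = 0.44. Exclusion then reports 0.50, further from no change.

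Tests: at n = 9, t = 0.58, 0.73 and 0.87 for k = 2, 3 and 5 (p = 0.58, 0.49, 0.41), and t approaches 1 as k grows. Under these assumptions the paired test is non-significant whichever set is used.

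**Part (b): urinalysis**

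No arithmetic applies. The eligibility-only premise of SAP 10.3 is set against the schedule. The extracted table has 14 visit columns, with urinalysis marks in columns 1, 6, 7, 12 and 14. Column 14 is the last one, Day 13 of the six-day cohort, and follows all dosing. Column 12 (Day 7) is not relied on, because the dosing row is also marked there although dosing ends on Day 6. One secure post-dose timepoint is enough to defeat the premise. It does not support a count of results left unsummarised.

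**The case against.** The strongest reply on (a) is that the SAP already settles it. The 9.4.1 sentence stands alone against protocol 9.3 and three places in the SAP, and an analyst working from the SAP would use the dosed set. That is largely right and limits the point to a contingent harm. It does not remove it, because the contradiction is also internal to the protocol and no precedence is stated.

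A reader might infer that the completer rule always pulls means toward no change and narrows SDs. The documents do not support that. It holds for a zero completer mean and a stopped subject more than about 1.06 SD away at n = 9. Someone stopped for a symptomatic toxicity need not be extreme on any given laboratory, vital-sign or ECG variable.

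A reader might also infer that AE incidence would be understated, for example 1 of 10 becoming 0 of 9. Protocol 9.4.4 and SAP 10.2 tabulate all AEs and those leading to study discontinuation, so the AE tables keep these subjects. Dose escalation is not touched: it rests on the single-dose cohorts and a committee review of all available data (7.5).

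On (b), the reply is that the results stay visible: protocol 9.4.8 and SAP section 7 list individual data, and clinically significant laboratory abnormalities are reported as AEs (9.4.4). That stands; with a cohort this small, little is hidden.

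A reader might further infer, by moving marks one column to the left, that the single-dose cohorts also have a Day 8 urinalysis. The table does not bear this out. In the dosing row, columns 2, 7, 8 and 9 are in place and only the last two marks look displaced. In the pregnancy row, compared with the timing in 8.2, column 7 itself is displaced. No common shift fits both rows, and a table damaged in extraction is not evidence about the plan. As extracted, the SAP's premise fits the single-dose cohorts.

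**Conclusion.** Both contradictions are real as written, and both are minor.

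(a) The completers sentence would exclude subjects for a reason related to outcome and could understate drug effects in the six-day cohort's change-from-baseline summaries. This needs three things: at least one dosed subject who stops early, post-dose data from that subject, and an analyst who follows 9.4.1 rather than the SAP. The shift in the mean is the stopped subject's distance from the completers divided by the number dosed: 0.33 SD for one subject 3 SD away among 9. That distance is assumed, and the direction is not fixed in advance. The effect is descriptive; no change in a significance test, an AE table or the single-dose cohorts is claimed.

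(b) SAP 10.3 drops a by-timepoint summary that protocol 9.4.2 specifies, on a premise that fails at least at Day 13 of the six-day cohort. What is lost is the summary, not the data.

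**What to change.** **Analysis set.** Delete the completers sentence from protocol 9.4.1. State that safety analyses use all subjects with at least one dose, as in SAP 5.2, including those who stop early or are replaced, and that PK and PD use their SAP populations. Align the ITT sentence in 9.3 with this. Until the protocol is amended, add one sentence to the SAP saying that its analysis populations govern.

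**Urinalysis.** Delete the two urinalysis sentences in SAP 10.3. Summarise urinalysis at every scheduled post-dose timepoint, in whichever cohorts it is collected: descriptive statistics for pH and specific gravity, and shift tables for the dipstick items, for which a mean and SD are not suitable.

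**Cost.** A few sentences and a few small tables from data already scheduled for collection. The protocol wording needs an amendment with IRB approval (Statement of Compliance). No visit, sample or clinical rule changes.
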